6.11.4. Clinical Laboratory Evaluation

Clinical laboratory assessments include hematology, serum chemistry, urinalysis, and safety-related immune markers such as neutrophil counts. All laboratory tests will be presented using the international system of unit (SI) when applicable.

Continuous laboratory tests will be summarized as changes from baseline to last observation for patients who have both baseline and at least one postbaseline result for Period 2 and 3, respectively:

- The scheduled visits/measurements will be included. The unscheduled visits and the repeat measurements will be excluded.
- For the Safety Population for Period 2, the comparisons between treatment groups will be conducted using an ANCOVA with treatment group and baseline value in the model.
- Data will be analyzed based on original scale.

Laboratory test observed values at each visit (starting at baseline) and change from baseline to each scheduled visit, respectively, will be displayed in box plots for patients who have both a baseline and at least one postbaseline result. These box plots will be used to evaluate trends over time and to assess a potential impact of outliers on central tendency summaries.

- The scheduled visits/measurements will be included. The unscheduled visits and the repeat measurements will be excluded.
- The following summary statistics will be included as a table below the box plot: number of patients with a baseline and at least one postbaseline result, mean, standard deviation, minimum, Q1, median, Q3, and maximum.
- Data will be summarized based on original scale.
- On the box plots of the laboratory test observed values, the lines of the reference ranges/limits (by using the performing laboratory reference ranges) will be added. In cases where limits vary across age and gender, the lowest of the high limits and the highest of the low limits will be used.

The number and percentage of patients with a treatment-emergent or follow-up emergent abnormal, high, or low for laboratory tests will be summarized by treatment group for each study period (Period 2 or 3 or 4). The comparisons between treatment groups will be conducted using Fisher's exact test for the Safety Population for Period 2.

- All scheduled, unscheduled and repeated measurements will be included.
- Performing laboratory will be used to defined the low and high limits reference ranges except for leukocyte, neutrophil, lymphocyte and platelet counts, where Lilly defined lower limit of normal will be used for these 4 labs.
- Alanine aminotransferase (ALT), aspartate aminotransferase (AST), total bilirubin, alkaline phosphatase (ALP), neutrophils, leukocytes, platelets, and lymphocytes will not be included in the treatment-emergent abnormal, high, or low summary as a separate analysis addressing the risk of liver injury is described in Section 6.11.3.1 and a separate analysis addressing Leukocytes (WBC) and Platelets is described in Section 6.11.4.1.
- Note that the ranges are defined by a lower limit of normal (LLN) and an upper limit of normal (ULN). A result that is greater than or equal to the LLN and less than or equal to the ULN is considered to be within the normal ranges.
- For categorical laboratory tests:
 - Treatment-emergent abnormal value is defined as a change from normal at all baseline visits to abnormal at any time postbaseline during the treatment period.
 - Follow-up emergent abnormal result is defined as a change from normal at baseline to abnormal at any time during the follow-up period.
- For continuous laboratory tests:
 - Treatment-emergent high value is defined as a change from a value less than or equal to the ULN at all baseline visits to a value greater than the ULN at any time postbaseline during the treatment period.
 - Treatment-emergent low value is defined as a change from a value greater than or equal to the LLN at all baseline visits to a value less than the LLN at any time postbaseline during the treatment period.
 - Follow-up emergent high value is defined as a change from a value less than or equal to the ULN at baseline to a value greater than the ULN at any time postbaseline during the follow-up period.
 - Follow-up emergent low value is defined as a change from a value greater than or equal to the LLN at baseline to a value less than the LLN at any time postbaseline during the follow-up period.
 - By-patient listing of abnormal laboratory test results (criteria defined in the shift tables excluding the normal category) for parameters of special interest (hepatic, leukocytes and platelets) will be provided.

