10.3.8.2. Clinical Laboratory Tests

Laboratory assessments will be presented as mean changes from baseline, and as incidence of treatment-emergent abnormal, high, or low laboratory values (see below). Shift tables will be presented for selected parameters.

- For categorical lab tests:
 - Treatment-emergent **abnormal** value = a change from normal at all baseline visits to abnormal at any time postbaseline.
- For continuous lab tests:
 - Treatment-emergent **high** value = a change from a value less than or equal to the high limit at all baseline visits to a value greater than the high limit at any time postbaseline.
 - Treatment-emergent **low** value = a change from a value greater than or equal to the low limit at all baseline visits to a value less than the low limit at any time postbaseline.

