6.11.4.1. Leukocytes (WBC) and Platelets

Further analyses will be conducted for total leukocytes, neutrophils, platelets, lymphocytes, monocytes, eosinophils, and basophils. Unless otherwise specified, neutrophils will be summarized as absolute neutrophils (derived by adding segmented neutrophils and band neutrophils).

Shift table will be produced showing the number and percentage of patients shifting from baseline to a minimum postbaseline result in each relevant category by treatment groups for study Periods 2 and 3, respectively:

- Scheduled visits, unscheduled visits, and repeat measurements will be included.
- Baseline is defined as the minimum result during the defined baseline period or baseline.
- Use the minimum non-missing postbaseline value within each study period.
- The parameters and categories are:
 - Leukocytes: $\geq 1 \times \text{LLN}$ (Normal), $< \text{LLN}$ to $\geq 3.0 \times 10^9/\text{L}$ (Grade 1), $< 3.0 \times 10^9/\text{L}$ to $\geq 2.0 \times 10^9/\text{L}$ (Grade 2), $< 2.0 \times 10^9/\text{L}$ to $\geq 1.0 \times 10^9/\text{L}$ (Grade 3), and $< 1.0 \times 10^9/\text{L}$ (Grade 4).
 - Neutrophils: $\geq 1 \times \text{LLN}$ (Normal), $< \text{LLN}$ to $\geq 1.5 \times 10^9/\text{L}$ (Grade 1), $< 1.5 \times 10^9/\text{L}$ to $\geq 1.0 \times 10^9/\text{L}$ (Grade 2), $< 1.0 \times 10^9/\text{L}$ to $\geq 0.5 \times 10^9/\text{L}$ (Grade 3), and $< 0.5 \times 10^9/\text{L}$ (Grade 4)
 - Platelets: $\geq 1 \times \text{LLN}$ (Normal), $< \text{LLN}$ to $\geq 75.0 \times 10^9/\text{L}$ (Grade 1), $< 75.0 \times 10^9/\text{L}$ to $\geq 50.0 \times 10^9/\text{L}$ (Grade 2), $< 50.0 \times 10^9/\text{L}$ to $\geq 25.0 \times 10^9/\text{L}$ (Grade 3), and $< 25.0 \times 10^9/\text{L}$ (Grade 4).
 - Lymphocytes: $\geq 1 \times \text{LLN}$ (Normal), $< \text{LLN}$ to $\geq 0.8 \times 10^9/\text{L}$ (Grade 1), $< 0.8 \times 10^9/\text{L}$ to $\geq 0.5 \times 10^9/\text{L}$ (Grade 2), $< 0.5 \times 10^9/\text{L}$ to $\geq 0.2 \times 10^9/\text{L}$ (Grade 3), and $< 0.2 \times 10^9/\text{L}$ (Grade 4).
- The above LLNs are defined as:
 - Leukocytes: $\text{LLN} = 4.0 \times 10^9/\text{L}$
 - Neutrophils: $\text{LLN} = 2.0 \times 10^9/\text{L}$
 - Platelets: $\text{LLN} = 150 \times 10^9/\text{L}$
 - Lymphocytes: $\text{LLN} = 1.1 \times 10^9/\text{L}$
- With additional categories:
 - Decreased; postbaseline category $<$ baseline category
 - Increased; postbaseline category $>$ baseline category

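### SAP 6.11.4 drops four blood counts from the treatment-emergent high summary by pointing to an analysis that covers only low values

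*SAP*

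**What the plan says.** Protocol 10.3.8.2 sets the general presentation: "Laboratory assessments will be presented as mean changes from baseline, and as incidence of treatment-emergent abnormal, high, or low laboratory values". Its definition of treatment-emergent high for a continuous test reads: "a change from a value less than or equal to the high limit at all baseline visits to a value greater than the high limit", on any later occasion. It exempts no analyte.

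SAP 6.11.4 keeps that definition and plans a summary of treatment-emergent and follow-up emergent values, with Fisher's exact test in Period 2. That summary includes scheduled, unscheduled and repeat results. A later bullet removes eight tests from the treatment-emergent part. They are ALT, AST, total bilirubin and ALP, together with the four blood counts; in the SAP's words, "neutrophils, leukocytes, platelets, and lymphocytes will not be included in the treatment-emergent abnormal, high, or low summary". For the counts, the reason given is that "a separate analysis addressing Leukocytes (WBC) and Platelets is described in Section 6.11.4.1".

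SAP 6.11.4.1 then specifies: "Shift table will be produced showing the number and percentage of patients shifting from baseline to a minimum postbaseline result". Two further rules apply: "Baseline is defined as the minimum result during the defined baseline period or baseline" and "Use the minimum non-missing postbaseline value within each study period". Normal means at or above the lower limit (4.0 for leukocytes, 2.0 for neutrophils, 150 for platelets and 1.1 for lymphocytes, all x10^9/L). Grades 1 to 4 all lie below that limit. The only other display in that section is a box plot of the change from minimum to minimum.

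The listing in SAP 6.11.4 is described as "By-patient listing of abnormal laboratory test results (criteria defined in the shift tables excluding the normal category"), for the hepatic, leukocyte and platelet parameters.

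**The concern.** The exclusion takes away two directions, high and low, and the section it points to gives back one. A patient whose count rises well above the upper limit is Normal in the shift table, does not meet the listing criteria and is absent from the high summary. The reason given in the SAP is therefore true for low values and untrue for high ones.

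What is at stake is a routine safety output: the between-arm incidence of high leukocytes, neutrophils, lymphocytes and platelets in the placebo-controlled period, and the corresponding summary in Period 3. The data are collected in any case, and these are core haematology counts for a drug whose adverse events of special interest include infections.

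**Working it through.** The plan states no figure to reproduce on this point. The check applies its rules to constructed patients and compares the sections.

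**Inputs.** The lower limits and the minimum-value rule come from SAP 6.11.4.1, the listing rule from SAP 6.11.4, and the definition of high from Protocol 10.3.8.2. Neither document gives an upper limit of normal (ULN) for the four counts, so I assumed a range for each. Units are x10^9/L.

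**Rules.**
- Shift table: compare the category of min(baseline) with the category of min(postbaseline).
- Listing: a result must fall in a category other than Normal.
- Treatment-emergent high: every baseline value ≤ ULN, and at least one postbaseline value > ULN.

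| Count | Baseline | Postbaseline | Minimum to minimum | Lower limit | Shift | Listed | Assumed ULN | High by protocol rule |
|---|---|---|---|---|---|---|---|---|
| Leukocytes | 6.5, 6.0 | 7.0, 25.0, 6.8 | 6.0 to 6.8 | 4.0 | Normal to Normal | No | 9–12 | Yes, throughout |
| Neutrophils | 4.0, 4.2 | 4.1, 20.0, 4.3 | 4.0 to 4.1 | 2.0 | Normal to Normal | No | 6–8 | Yes, throughout |
| Platelets | 250, 240 | 260, 900, 255 | 240 to 255 | 150 | Normal to Normal | No | 300–450 | Yes, throughout |
| Lymphocytes | 2.0, 1.9 | 2.1, 12.0, 2.0 | 1.9 to 2.0 | 1.1 | Normal to Normal | No | 3–5 | Yes, throughout |

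Under the SAP text, 0 of 4 are counted and 0 of 4 are listed. Under the protocol definition, 4 of 4 are counted. The Increased row of the shift table does not help, because it compares the same minimum-based categories and there is no level above Normal.

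**What other displays would show for the leukocyte patient.** Reading the values in time order, change to last observation is 6.8 − 6.0 = +0.8, so the peak of 25.0 does not enter. If the peak fell at a scheduled visit, it would contribute to that visit's box plot, which carries reference lines and reports the maximum. If it came from an unscheduled or repeat sample, it would not appear there. The listing of infection events in SAP Table RHCH.6.7 carries minimum counts for Period 2 only.

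**Comparison within the SAP.** The same bullet removes the four liver tests, but the hepatic analyses in Table RHCH.6.7 use maximum postbaseline values against the ULN, so their high direction is kept. Monocytes, eosinophils and basophils are not excluded and keep a treatment-emergent high count. Total leukocytes and neutrophils do not.

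**Extent.** In the Schedule of Activities, haematology is drawn after baseline at Weeks 4, 8, 12 and 16 (4 draws) and at Weeks 20, 24, 28, 32, 36, 44 and 52 (7 draws): 4 + 7 = 11 scheduled draws for each of four analytes.

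**The case against.** The strongest reply is that the low-direction focus is deliberate. The haematological events of special interest in Protocol 9.2.2 are cytopenias, and the blood-count eligibility limits, discontinuation thresholds and neutrophil monitoring rules all concern low counts. Infections are analysed directly in Table RHCH.6.7, with Fisher's exact test in Period 2 and a listing of anti-infective use. Clinically significant laboratory findings that lead to a diagnosis are reported as adverse events. Patient-level safety does not depend on this table, and neither document names high counts as a particular concern. All of this stands, and it keeps the point small. It supports adding a minimum-based analysis. It does not support the reason the SAP actually gives, which is that the counts are covered elsewhere.

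Three stronger readings are tempting, and the documents do not support them.

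- A reader might infer that SAP 6.11.4 contradicts itself, because the bullet before the exclusion sets sponsor-defined lower limits for these same four counts. It need not: the exclusion names only the treatment-emergent summary, so those limits can still serve follow-up emergent low values in Period 4.
- A reader might infer a breach of the protocol. Protocol 10.3.8 leaves further safety detail to the SAP, and Protocol 10.3 requires an amendment only when a principal feature changes; other changes and their justification go in the clinical study report. This is a narrowing.
- A reader might infer that high counts vanish from the report. They remain visible in the box plots, and they contribute to mean change where the high value is the last observation.

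**Conclusion.** The point holds as a minor correction to the safety tables. For leukocytes, neutrophils, lymphocytes and platelets, the SAP produces no patient count of treatment-emergent high values in Period 2 or Period 3 and no Fisher comparison in Period 2, and its listing criteria omit such values. That is narrower than Protocol 10.3.8.2, and the coverage the SAP relies on exists for low values only.

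The conclusion rests on the wording of the two SAP sections and does not depend on the assumed upper limits, which only illustrate it. The 11 draws count opportunities for a high value. The documents give no basis for estimating how often one would occur, so no effect on the safety conclusions can be quantified. Efficacy results, type I error and blinding are untouched.

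**What to change.** In SAP 6.11.4, limit the exclusion of the four counts to the treatment-emergent low direction. Keep them in the treatment-emergent high summary against the performing laboratory's upper limit, with Fisher's exact test in Period 2 and a descriptive summary in Period 3. Because SAP 6.11.4.1 derives absolute neutrophils as segmented plus band cells, the SAP should also say which upper limit applies to that sum.

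Adding values above the upper limit to the by-patient listing is optional. If the sponsor prefers to leave the high direction out, the SAP should give that as the decision in place of the cross-reference, and the clinical study report should describe and justify it.

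The cost is a wording change and four rows in a table already planned, plus extra listing lines if that option is taken. No new data are needed.

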9.4.10.2.3. Post-Treatment Follow-Up Period

At Visit 801 and V802, the following monitoring applies:

- As long as a patient's neutrophil count is <1000 cells/ μL ($<1.00 \times 10^3/\mu\text{L}$ or <1.00 GI/L) at any follow-up visit, the patient is to return for visits at least Q4W (may require unscheduled visits).
- As long as a patient's neutrophil count is ≥ 1000 cells/ μL and <1500 cells/ μL ($\geq 1.00 \times 10^3/\mu\text{L}$ and $<1.50 \times 10^3/\mu\text{L}$ or ≥ 1.00 GI/L and <1.50 GI/L) at any follow-up visit, the patient is to return for additional visit(s) at least every 4 to 8 weeks (may require unscheduled visits).

If, at Visit 802, the patient's neutrophil count remains <1500 cells/ μL ($<1.50 \times 10^3/\mu\text{L}$ or <1.50 GI/L) and less than the patient's baseline neutrophil count, or if the investigator deems additional follow-up may be necessary, the investigator will determine the appropriate management of the patient and the appropriate timing of additional contact(s).

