6.11.3.1. Special Safety Topics including Adverse Events of Special Interest

Safety information on special topics including AEs of special interest (AESI) will be presented by treatment group and by study period. [Table RHCH.6.7](#) provides the definitions/derivations and analyses methods (including analyses, summaries and by-patient listings) of special safety topics including AESIs.

Potential AESIs will be identified by a standardized MedDRA query (SMQ) or a Lilly-defined MedDRA PT listing. Preferred terms within an SMQ will be classified as broad and narrow. In the Lilly-defined MedDRA PT listings, Lilly has provided the broad and narrow classification. The Lilly-defined broad terms are for a more sensitive search of potential events of interest and the Lilly-defined narrow terms are for a more specific search. Therefore, the summaries will include the classifications of broad term (same as pooling narrow and broad terms together) and narrow term.

In the event that the listing of terms or analysis changes for a special safety topic, it will be documented in the program safety analysis plan (PSAP) which will supersede this document; it will not warrant an amendment to the individual study SAP. For final analysis, the most current version of PSAP will be used, including PSAP released after SAP finalization but before database lock.

For Period 3, summaries will be provided for the Extended Treatment Period Population. In addition, for Combined Periods 2 and 3 on ixekizumab treatment only, selective summaries will be provided for the All Ixekizumab Exposures Safety Population.

In general, AESI summary will not be provided for Follow-Up Population during Period 4 except hepatic laboratory tests.

Table RHCH.6.7. Definitions and Analyses of Special Safety Topics including Adverse Events of Special Interest

Special Safety Topic	Definition / Derivation	Analysis / Summary / Listing

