	
 ○ The analysis of 2× ULN will contain 5 subsets: patients whose non-missing maximum baseline value is ≤1× ULN, >1× ULN to <1.5× ULN, ≥1.5× ULN to <2× ULN, ≥2× ULN, or missing. • Alkaline phosphatase (ALP): maximum postbaseline measurement >1.5 times (1.5×) the Performing Lab ULN for all patients with a postbaseline value, and divided into 4 subsets: patients whose non-missing maximum baseline value is ≤1× ULN, >1× ULN to ≤1.5× ULN, >1.5× ULN, or missing. 	
	
Shift for ALT, AST, ALP and total bilirubin from maximum baseline to maximum postbaseline will be produced with the requirements using Performing Lab Reference Ranges:
 
 • Include scheduled visits, unscheduled visits, and repeat measurements. • Use the maximum non-missing value in the baseline period. • Use the maximum non-missing postbaseline value within each study period. • Categories are: 
 ○ ALT: ≤1× ULN, >1 to <3× ULN, ≥3 to <5× ULN, ≥5 to <10× ULN, ≥10 to <20× ULN, and ≥20× ULN ○ AST: ≤1× ULN, >1 to <3× ULN, ≥3 to <5× ULN, ≥5 to <10× ULN, ≥10× to <20× ULN and ≥20× ULN ○ Total bilirubin: ≤1× ULN, >1 to <1.5× ULN, ≥1.5 to <2× ULN, ≥2× ULN ○ ALP: ≤1× ULN, >1 to ≤1.5× ULN, >1.5× ULN • With additional categories: 
 ○ Decreased: postbaseline category < baseline category ○ Increased: postbaseline category > baseline category ○ Same: postbaseline category = baseline category 	
Period 2, Period 3 (Summary) : Shifts from maximum baseline to maximum postbaseline category

	
Elevated hepatic criteria: maximum ALT ≥3× ULN and maximum total bilirubin ≥2× ULN using Performing Lab Reference Ranges.
 
Listing of patients who meet any of the following criteria:
 
 • Elevated hepatic criteria: defined as maximum ALT ≥3× ULN and maximum total bilirubin ≥2× ULN • An ALT or AST ≥3× ULN • An alkaline phosphatase (ALP) >1.5× ULN • A total bilirubin ≥2× ULN 
The listing will include: patient demographics, concomitant medications, ALT/AST/ALP/total bilirubin/GGT by visit, treatment start and stop dates, and reason for treatment discontinuation.
	
Period 2 (Fisher’s exact test), Period 3, and Period 4 (Summary): Elevated hepatic criteria
 
Listing: Elevations in hepatic laboratory tests

Special Safety Topic	Definition / Derivation	Analysis / Summary / Listing

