6.11.4.2. Neutrophil Follow-Up

Neutrophil counts will be followed throughout the study. The neutrophil follow-up analysis will be conducted on the Neutrophil Follow-Up Population defined as patients who have an absolute neutrophil count < 1500 cells/ μL (SI units: $< 1.5 \times 10^9/\text{L}$) at the last scheduled visit or early termination visit prior to entering Period 4 and less than the patient's baseline absolute neutrophil count (that is, prior to first injection at Week 0).

Neutrophil clinical recovery is defined as an absolute neutrophil count ≥ 1500 cells/ μL (SI units: $\geq 1.5 \times 10^9/\text{L}$) or greater than or equal to a patient's minimum absolute neutrophil count prior to first study drug injection at Week 0. If a patient's neutrophil count has not recovered within 12 weeks after entering the follow-up period (Visit 802), the investigator will determine the appropriate management of the patient and the appropriate timing of additional contact(s).

The number and percentage of patients achieving neutrophil clinical recovery will be presented by treatment groups and week interval for the Neutrophil Follow-Up Population for Period 4. The number and percentage of patients with an absolute neutrophil cell count that is at least 25%,

50%, 75%, or 100% of the patient's baseline absolute neutrophil count (that is, prior to first injection at Week 0), irrespective of absolute neutrophil minimum, will be included in the summary.

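### Eight blood-cell and liver analytes are taken out of the emergent-abnormality summary because other analyses cover them, but in Period 4 those analyses largely do not, and worsening from an already abnormal entry value is not counted on any reading

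*SAP*

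**What the plan says.** SAP 6.11.4 sets up one summary. The number and percentage of patients with "treatment-emergent or follow-up emergent abnormal, high, or low for laboratory tests will be summarized by treatment group" is planned "for each study period (Period 2 or 3 or 4"). In the bullets beneath it:

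- The four cell counts (leukocytes, neutrophils, lymphocytes, platelets) are to be judged against sponsor-defined lower limits.
- The next bullet says that these four counts and ALT, AST, total bilirubin and ALP "will not be included in the treatment-emergent abnormal, high, or low summary as a separate analysis addressing the risk of liver injury" is in SAP 6.11.3.1, with a second analysis for leukocytes and platelets in SAP 6.11.4.1.
- Treatment-emergent and follow-up emergent values are then defined separately. A follow-up emergent low needs a value at or above LLN at baseline. A follow-up emergent high needs a value at or below ULN at baseline. SAP 6.1.4 sets the Period 4 baseline as the last non-missing value on or before entry to that period.

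The separate analyses have these scopes:

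- SAP 6.11.4.1: a shift to the "minimum postbaseline result in each relevant category by treatment groups for study Periods 2 and 3, respectively". The box plots there are also for Periods 2 and 3.
- SAP 6.11.4.2: neutrophil recovery in Period 4, restricted to patients below 1500 cells/µL "at the last scheduled visit or early termination visit prior to entering Period 4 and less than" their own baseline.
- SAP Table RHCH.6.7, Hepatic: single-analyte elevations and shifts for Periods 2 and 3. Only the joint ALT and bilirubin criterion goes further: "Period 3, and Period 4 (Summary): Elevated hepatic criteria".
- SAP 6.11.3.1, text: as a general rule, "AESI summary will not be provided for Follow-Up Population during Period 4 except hepatic laboratory tests".

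**The concern.** The exclusion rests on a reason, namely that the eight analytes are tabulated elsewhere. That is so for Periods 2 and 3. For Period 4 it is largely not so, yet the summary from which they are removed also covers Period 4.

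The analytes matter. Leukopenia, neutropenia, thrombocytopenia and liver enzyme changes are the first two entries in the protocol's list of adverse events of special interest (protocol 9.2.2), and all eight analytes have numeric limits among the discontinuation criteria (protocol 8.1.1). Protocol 9.4.10.2.3 also attaches action to follow-up counts: with neutrophils below 1000 cells/µL "at any follow-up visit, the patient is to return for visits at least Q4W". A follow-up report that cannot say how many patients reached that level, or had a single enzyme rise to several times ULN, would lack the figures that the follow-up sampling was designed to give.

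**Working it through.** No formula or sample size enters here. The check maps each analyte to every Period 4 output that the SAP plans.

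**Step 1. Period coverage of each tabulated analysis**

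| Analysis (SAP) | Periods 2 and 3 | Period 4 |
|---|---|---|
| Cell-count shifts and box plots (6.11.4.1) | yes | no |
| Single-analyte hepatic elevations (Table RHCH.6.7) | yes | no |
| Hepatic shifts (Table RHCH.6.7) | yes | no |
| Joint ALT and bilirubin criterion (Table RHCH.6.7) | yes | yes |
| Neutrophil recovery (6.11.4.2) | no | yes, only in patients already below 1500 cells/µL and below their own baseline |
| Emergent high/low summary (6.11.4) | excluded for the eight | depends on the reading |

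**Step 2. The two readings of the exclusion**

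- *Wide reading* (the bullet governs the whole summary above it): 0 of 4 cell counts and 0 of 4 hepatic analytes have their own tabulated incidence in Period 4.
- *Literal reading* (the bullet removes treatment-emergent results only): 8 of 8 stay in the follow-up emergent summary, counted as crossings of LLN or ULN from a normal Period 4 baseline.

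On either reading, 0 of 8 is tabulated singly in Period 4 by grade or by multiple of ULN.

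**Step 3. Test cases under each reading**

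The neutrophil LLN is taken as 2.0 × 10⁹/L, that is 2000 cells/µL, from SAP 6.11.4.1.

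| Entry to Period 4, then follow-up | Wide | Literal |
|---|---|---|
| Neutrophils 2500, then 900 cells/µL | not counted | counted: 2500 ≥ 2000, and 900 < 2000 |
| Neutrophils 1800, then 900 cells/µL | not counted | not counted |
| ALT 1.2 × ULN, then 6 × ULN, bilirubin normal | not counted | not counted |

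In the second case, 1800 < 2000, so the entry value is already below LLN and the fall cannot be follow-up emergent. Since 1800 ≥ 1500, the patient is also outside the Neutrophil Follow-Up Population. By the categories of SAP 6.11.4.1 this is a move from Grade 1 (below LLN to 1.5 × 10⁹/L) to Grade 3 (below 1.0 to 0.5 × 10⁹/L). The same applies to any patient who enters at 1500 to 1999 cells/µL and then worsens.

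In the third case, 1.2 × ULN exceeds ULN at baseline, so the rise is not follow-up emergent. Normal bilirubin means that the joint criterion is not met. In Table RHCH.6.7 this would be a move from the category above 1 and below 3 × ULN to the category from 5 to below 10 × ULN, but that table has no Period 4 version.

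**Step 4. Text against table.** The text of SAP 6.11.3.1 exempts hepatic laboratory tests in general from the rule of no Period 4 summary. Table RHCH.6.7 delivers only the joint criterion in Period 4. The two need to be reconciled.

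**The case against.** The best defence is the wording. The bullet names the treatment-emergent summary only, while SAP 6.11.4 defines follow-up emergent values separately and SAP 6.11.5 keeps the same distinction for vital signs. The sponsor lower limits for the four cell counts have a use in this summary only if those counts stay in some part of it. On that view all eight analytes keep a Period 4 incidence, and SAP 6.1.4 promises descriptive summaries of follow-up safety data in any case. This stands as the better reading. It does not settle the matter, because the bullet sits under a single summary covering both kinds of result, and a programmer could reasonably drop the eight throughout. Nor does it help the second and third cases above.

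Other outputs also reach Period 4. Follow-up emergent adverse events and serious adverse events are tabulated by preferred term (SAP 6.11.2 and 6.11.3), and the by-patient listings of abnormal hepatic, leukocyte and platelet results carry no period limit. These reduce the gap but do not close it. A listing gives no count or denominator, and under protocol 9.4.3 a laboratory finding has to be reported as an adverse event when it is clinically significant and results in a diagnosis.

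Finally, SAP 6.11.3.1 lets the program safety analysis plan supersede it where a special-topic analysis changes. That plan is not among the documents, so it may already add Period 4 tables.

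A reader might infer that new cytopenias and enzyme rises in follow-up have no incidence at all, or that every separate analysis stops at Period 3. The documents do not support either. The first holds only on the wide reading, and the joint hepatic criterion and neutrophil recovery are both tabulated in Period 4. Nor does the gap mean that patients go unmonitored: hematology and serum chemistry are scheduled at Visits 801 and 802.

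**Conclusion.** The concern holds as a gap in tabulation with an ambiguity on top. The reason given for excluding the eight analytes is not valid for Period 4, where the only separate tabulations are the joint ALT and bilirubin criterion and neutrophil recovery in patients already low. Depending on the reading, either 0 or 8 of the eight analytes keep a Period 4 incidence of crossing LLN or ULN. On both readings, worsening from an already abnormal entry value goes uncounted, and no single analyte is tabulated by grade or multiple of ULN.

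This rests on two assumptions: that the sponsor lower limits mentioned in SAP 6.11.4 are those listed in SAP 6.11.4.1, and that the program safety analysis plan does not already supply the missing tables. The documents give no rate of follow-up abnormalities, so the number of patients affected cannot be stated. No efficacy result and no between-group safety comparison is touched, since Period 4 is descriptive. The change is still worth making, because these are named safety topics and the data will already be in hand.

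**What to change.** 1. In SAP 6.11.4, state that the exclusion of the eight analytes applies to Periods 2 and 3 only, and that all eight remain in the Period 4 follow-up emergent summary, with the sponsor lower limits for the four cell counts.
2. Add Period 4 to the shift table in SAP 6.11.4.1 and to the single-analyte hepatic elevation and shift tables in Table RHCH.6.7. This closes the gap that item 1 alone leaves open, and brings the table into line with the hepatic exception in the text of SAP 6.11.3.1.
3. Beside the Neutrophil Follow-Up Population, report the number of patients whose first neutrophil count below 1500 cells/µL occurs in Period 4.

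The cost is a sentence in the SAP and a few descriptive tables from samples already scheduled at Visits 801 and 802. No new sampling and no change to patient management is involved.
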